1.1 Executive Summary

Globally, childhood mortality has shown a promising downward trend in recent years, however, many sub-Saharan countries still have relatively high child mortality rates. In previous studies within Niger, Tanzania, and Malawi, mass azithromycin treatment to children aged 1-59 months old effectively reduced all-cause childhood mortality¹. A similar study will be conducted in Burkina Faso to replicate the results of mass azithromycin treatment.

We propose an individually randomized placebo-controlled trial alongside the MORDOR II Burkina Faso trial to evaluate the effect of a single dose of azithromycin (20 mg/kg) on potential mediators of the effect of azithromycin on all-cause mortality. Many questions surround the mechanism behind azithromycin's effect on reducing childhood mortality. Further questions exist regarding antibiotic resistance and how mass antibiotic administration can impact intestinal microflora. The goal of this study is to demonstrate the changes in the gut microbiome after antibiotic administration and to measure the growth of children after receiving a single dose of azithromycin. Additionally we will measure resistance markers, inflammatory markers, and IgA-bound bacteria throughout the study. We hypothesize that a single dose of azithromycin will lead to a significant increase in child growth and that the gut microbiome will be significantly different in children who received azithromycin compared to those who received placebo.

1.2 Objectives

1:

To determine the effect of a single dose of azithromycin for children aged 8 days-59 months on longitudinal changes in the intestinal microbiome over a 6-month period. We hypothesize that a single dose of azithromycin will result in a significant difference in the intestinal microbiome within the treatment group compared to the placebo group after a 6-month period within children ages 8 days-59 months.

2:

To determine the effect of a single dose of azithromycin for children aged 8 days-59 months on child growth over a 6- month period. We hypothesize that a single dose of azithromycin will increase child growth over a 6-month period in children aged 8 days-59 months.

3.

To determine the effect of a single dose of azithromycin for children aged 8 days to 59 months on the presence of macrolide genetic resistance determinants within the first two weeks post-

treatment. The investigators hypothesize that a single dose of azithromycin will increase the presence of macrolide resistance determinants over a 2-week period in children aged 8 days to 59 months.

1.3 Study Partners

CRSN and UCSF are equal partners in the production of this protocol. This study was designed together and will be implemented by both parties. The Bill and Melinda Gates Foundation is providing funding for this study.

1.4 Study Site

This study will be conducted in the northwestern region of Burkina Faso in the town of Nouna. Nouna is approximately 300 kilometers from the capital city of Ouagadougou. Nouna town has a population of approximately 28,000 which includes about 4,600 pre-school aged children. There is currently a hospital that serves all 7 sectors of Nouna town. We will enroll up to 1500 children presenting to the hospital.

2 Chapter 2: Context

2.1 Background

Our previous MORDOR I research demonstrated a significant reduction in all-cause child mortality after biannual mass azithromycin distribution. In three sub-Saharan Africa countries, (including Niger, Tanzania, and Malawi) mass azithromycin treatment over 2 years resulted in a 14% reduction in child mortality. Moreover, 1 in 5-6 deaths were shown to be averted within Niger alone¹. Similar findings were demonstrated in a previous study for trachoma control in Ethiopia with mass azithromycin distribution. This study in rural Ethiopia noted a nearly 50% decrease in all-cause childhood mortality⁵. However, neither of these studies evaluated the longitudinal impact azithromycin has on the gut microbiome. The MORDOR II trial in Burkina Faso will further evaluate the efficacy of biannual azithromycin treatment. The under-5 child mortality rate in Burkina Faso is approximately 110 per 1,000 live births. Major causes of child mortality in this area are infectious mostly due to malaria, diarrhea, and upper respiratory tract infections³. In addition, malnutrition contributes to a high burden of child mortality and morbidity within this region as well⁴. By treating underlying conditions, the use of routine antibiotic treatment could reduce diverse health outcomes leading to morbidity and mortality. We propose to conduct this study alongside the MORDOR II trial in the town of Nouna where a majority of childhood deaths are attributable to infectious causes and malnutrition.

The World Health Organization is considering adopting the presumptive use of azithromycin and other antibiotics as a recommendation to reduce childhood mortality in areas with a high infectious disease burden². Many questions remain unanswered surrounding the use of mass antibiotic treatment in areas with high child morbidity and mortality. This study will add to the current knowledge of mass azithromycin distribution from our previous MORDOR I research. We propose to evaluate how azithromycin will impact childhood growth and to assess the changes that occur in the intestinal microbiome following a single dose of azithromycin treatment. The goal is to contribute more scientific literature that could assist future guidelines regarding antibiotic use.

The role of antibiotics on child growth is unclear. Recent studies indicate that antibiotic use could impact child growth, but a previous study in Niger failed to find a statistically significant correlation between antibiotic treatment with azithromycin and stunting, underweight, or MUAC of pre-school aged children. Longitudinal studies have been recommended to further investigate the role of antibiotics on child growth⁶. Meanwhile some studies suggest antibiotics may create modifications in the gut microbiota impacting nutrient absorption and weight gain⁷. We propose to measure child growth through anthropometric measurements longitudinally over a 6-month period to see if azithromycin treatment impacts child development. We hypothesize that children receiving a dose of azithromycin will have more growth and development in terms of height, weight, and mid-upper arm circumference compared to children who receive placebo.

We propose a longitudinal study designed to improve our knowledge about the changes in the intestinal microbiome following the course of a single dose of antibiotic in a setting with high childhood mortality and morbidity. More specifically, we propose to follow 450 children for a 6-month time period that are between the ages of 8 days old and 59 months old. Children in this age bracket are at the highest risk for mortality from infectious causes, and furthermore, they are at the highest risk for malnutrition. This group of children would receive the greatest benefit from this intervention. The causal changes in the microbiome are vastly understudied in regards to changes in the gut microbiome following a course of antibiotics. We hypothesize that children receiving a dose of azithromycin will have a higher prevalence of anti-pneumococcal bacterial resistance in nasopharyngeal samples, decreased bacterial diversity, and a higher likelihood of identification of bacterial resistance genes in stool and nasopharyngeal samples.

3 Chapter 3: Study Design

We propose to prospectively follow 1500 children treated with azithromycin or placebo for 6 months in the town of Nouna. Our goal is to evaluate intestinal microbiome changes and child growth longitudinally. We will individually randomize eligible children to a single dose of

azithromycin or placebo at the Nouna town hospital. At days 0, 14, 180, and at 2 years post enrollment we will collect a series of samples to measure both outcomes. Anthropometry and vital status will be collected at each follow up visit. In addition, we will collect a blood smear at each visit, record body core temperature, collect a nasopharyngeal swab, a rectal swab, fresh frozen stool, and perform whole blood venipuncture. We will also randomly select 25 children per arm (n=50) to receive a rectal swab at days 0, 2, 4, 6, 8, 10, 12, 14, and 180 days after treatment. As per the Bill and Melinda Gates Foundation guidelines, all biological samples collected will be stored and made available to other investigators at the finish of the study.

GAMIN:

Azithromycin	Placebo
n=725	n=725

Supplementary rectal swab group:

Azithromycin	Placebo
n=25	n=25

3.1 Recruitment and Eligibility

3.1.1 Recruitment

Prior to enrollment in the study, mobilization will be conducted in up to four secteurs of Nouna Town (administrative districts). The mobilization will be done house-to-house within the designated secteurs. Caregivers with children under 59 months will be invited to participate. All study activities will take place at a local primary hospital. Community mobilizers will inform caregivers where to go for enrollment in the trial. Enrollment will occur at the Nouna hospital.

At the hospital, a dedicated study team member will enroll the child. The study team member will be an existing member of the enrollment site staff who will be trained for the study or an external study team member who will be placed at the site for the duration of the study. Trained staff will collect the biological specimens. The team member will verify consent from the parent

or guardian and review the eligibility of the child. Following enrollment, each child will be provided with a study card and unique identification number to be entered in the tablet at each follow-up visit.

3.1.2 Eligibility

Eligible children for this study are those who are at least 8 days old but younger than 59 months old. Child must live within Nouna town and report to the local Nouna town hospital during the study period.

Inclusion Criteria

- Between 8 days and 59 months old
- Primary residence within catchment area of study site
- Available for full 6 month study
- No allergy to macrolides/azalides
- Appropriate written informed consent from at least one parent or guardian
- Able to feed orally
- No prior enrollment in the NAITRE study

Exclusion Criteria

- <8 days old or >59 months
- Primary residence outside catchment area of study site
- Not available for full 6 month study
- Known allergy to macrolides/azalides
- No written informed consent from at least one parent or guardian
- Unable to feed orally
- Prior enrollment in the NAITRE study

3.2 Sample Size

We will enroll up to 1500 children into the two study arms (725/arm). In the sub-study, 25 children per arm will be randomized. This sample size is based on the primary outcome, Simpson's alpha diversity in the intestinal microbiome. We will base some statistical assumptions on preliminary data from the Nouna HDSS. For instance, we assume a 15% loss to follow-up, a baseline effective number of 9, and a standard deviation of 0.7.

3.3 Baseline Measurement

After enrollment and informed consent but prior to randomization, baseline samples will be collected. Children will undergo anthropometry (height, weight, mid-upper arm circumference), whole blood venipuncture, a finger prick for malaria blood smears, 2 NP swabs, a rectal swab and they will provide a fresh frozen stool. In addition, study staff will administer a baseline questionnaire inquiring about the child's age and sex as well as the mother's maternal age, education, number of children, and breastfeeding.

3.4 Randomization

A list of potentially eligible children will be asked a series of questions to determine their eligibility. After completion of the baseline assessment, children will be randomized to receive a single dose of directly observed oral azithromycin or placebo.

UCSF investigators will generate the randomization sequence. Children will be randomized in a 1:1 fashion to a single dose of azithromycin or placebo.

This study will be a double blind study to both the participants and the staff (both Nouna and UCSF).

After consent is obtained, the hospital worker will enter the child's information into a computer tablet or smart phone. The application "Survey Solutions" will be installed on the computer. The application will ask the hospital worker if consent has been obtained and information to determine the child's eligibility status. Once the child is determined fully eligible for the study, the application will tell the health worker which treatment letter to provide the child with. For example, the screen on the tablet may say "treat with AA" or "treat with BB". The hospital will be equipped with bottles of azithromycin donated from Pfizer that will be pre-labeled with treatment letters such as AA or BB. The application will be pre-programmed with the randomization scheme, but study staff and participants will remain blinded.

3.5 Outcomes

Primary Outcome

- **Changes in intestinal microbiome over a 6-month period (Objective 1).** Microbiome diversity will be measured at all follow-up time points.
 - **Whole Blood Venipuncture.** Whole blood venipuncture will be collected at all follow-ups. We will measure cell-free DNA and inflammatory markers such as C-reactive protein.
 - **Nasopharyngeal Swabs.** NP swabs will be collected at all follow-up time points. We will collect data on phenotypic resistance of *S. pneumoniae*, evaluate the microbiome using next-generation sequencing, and monitor genotypic resistance among various organisms.
 - **Fresh Frozen Stool.** FFS will be collected at all follow-ups. We will be looking for IgA-bound bacteria from the small intestine and evaluating inflammatory markers such as C-reactive protein.

[figure not shown]
- **Rectal Swabs.** We will collect rectal swabs at all time points. We will monitor genotypic resistance of various organisms with targeted PCR and evaluate the microbiome using next-generation sequencing.
- **Presence of macrolide genetic resistant determinants (Objective 3).** Macrolide resistance will be measured from a sample of participants.
 - **Rectal Swab Cohort.** We will collect rectal swabs from 50 children at days 0, 2, 4, 6, 8, 10, 12, 14 and 180 post-treatment. Macrolide resistance will be analyzed using DNA sequencing.
 - **2 Year Timepoint.** We will collect rectal swabs from all kids 2 years post-enrollment to evaluate macrolide genetic resistance determinants.

Secondary Outcomes

- **Child growth over a 6-month period (Objective 2).** Anthropometry measurements will be collected at all follow-up time points. Weight gain will be defined as grams per kilogram per month (g/kg/month).
 - **MUAC.** Mid-upper arm circumference will be measured at all follow-ups
 - **WAZ.** Weight will be measured at all follow-ups and weight-for-age z-scores will be calculated
 - **WHZ.** Weight and height will be used to calculate weight for height z-scores
 - **HAZ.** Height or length will be measured at all follow-ups and height-for-age z-scores will be calculated.
- **Mortality by 6-months.** Vital status will be assessed at all follow-up visits. Mortality will be defined as death within the study period. Date of death will be collected.
- **Adverse events.** Adverse events will be reported at all follow-ups.
- **Malaria.** Thin and thick smears will be collected at all follow-up time points to determine malaria status. Additionally, we will measure each child's core body temperature.
- **PERMANOVA L-1, L-2.** Norm distance on bacterial reads (intestinal) for 50 children within the first 2 weeks post-treatment.
- **Campylobacter.** Changes in normalized reads for Campylobacter species will be evaluated using DNA-seq from rectal swabs of 50 kids collected within the first 2 weeks after treatment.
- **Resistome.** Chao1 total resistance gene determinant richness using DNA-sequencing from rectal swabs of 50 kids collected within 2 weeks after treatment.

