4.11 Summary of Sample Collections

Summary of laboratory and other assessments in Nouna longitudinal study

Organism/Outcome	Test	Sample	Time Point (Days)			Processing Site
			0	14	180	
Malaria	Thick and Thin Blood Smears	Finger stick	✓	✓	✓	Nouna
Phenotypic resistance: S. pneumoniae	Kirby Bauer (or Etest)	NP swabs	✓	✓	✓	Nouna
Genotypic resistance: E. coli , S. pneumoniae , S. aureus , Campylobacter spp Klebsiella spp	Targeted PCR: erm , mef , mph	Rectal and NP swabs	✓	✓	✓	UCSF
Microbiome	Next-generation sequencing	Rectal and NP swabs	✓	✓	✓	UCSF
Inflammatory markers	C-reactive protein	Whole blood and frozen stool	✓	✓	✓	Nouna and/or Gates labs
IgA-bound bacteria from small intestine	BugFACS	Whole blood and frozen stool	✓	✓	✓	Gates labs
Nutritional status	Anthropometric measurements	Weight, height, MUAC	✓	✓	✓	Nouna
Vital status	Mortality, hospitalization	Caregiver questionnaire		✓	✓	Nouna

5 Chapter 5: Study Medication

Enrolled participants will be offered weight-based, directly observed, oral suspension azithromycin or placebo. Adverse events will be monitored.

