6.2 Rectal Swab Collection for Culturing/Microbiological Testing

Rectal swabs are collected at baseline, day 14, day 180, and 2 years after treatment. A small cohort of 50 randomly selected children will receive an additional rectal swab on days 0, 2, 4, 6, 8, 10, 12, and 180 post treatment..

The test will require that the child's parent and examiners work together to obtain a good sample. Is it important to describe the test to the parent so that they can best assist with keeping the child still during the procedure, if necessary.

In place of stool specimens, rectal swabs can be collected in the following way:

1. Put on a clean pair of gloves.
2. Partially open the fecal swab package and remove the top section of the collection vial (this can be discarded).
3. Position the child:
 - Lie the child on his/her back, hold legs in the air (it is useful to have assistance).
 - Or have the child lay on his/her stomach across the mother/guardian's lap
4. Remove the swab from the package. Take care that the cotton tip is not touched. If it is touched, throw the swab away and begin with a new one.
5. Insert the tip of the swab into the child's anus only as far as needed to contact fecal material (1-3cm) and rotate 180 degrees. The tip should be a brownish color when removed.
6. Place swab into the preservative in the collection tube. Make sure the swab is fully submerged in the liquid preservative and then break the swab off using the pre-scored breaking point.
7. Screw the cap back on the tube and make sure that it's tightened. Wrap the area where the cap meets the tube with Parafilm to ensure that the sample will not leak, and then place the tube into the appropriate sample box.
 - If the swab cannot be broken off while the tip is fully submerged in the liquid, try twirling the swab in the liquid first (to release the contents of the sample into the preservative) before breaking it off. Avoid rubbing the sample on the tip of the swab off on the side of the tube where there is no liquid.
8. Place a random number label on the collection tube.
9. Place the tube the rectal swab container.
10. **Swab storage for Genetic analysis:** Store samples at room temperature. According to the manufacturer, the preservative in the tube will preserve DNA for 5 months at room

temperature (7 days for RNA), and thereafter can be frozen (-20°C or -80°C) for long-term storage.

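### Objective 3's two-week macrolide-resistance test is assigned only to 25 children per arm, although erm/mef/mph PCR on main-trial rectal swabs at days 0 and 14 is already scheduled and the SAP has no resistance analysis

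*Protocol*

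**What the plan says.** Protocol 1.2 states the Objective 3 hypothesis: "The investigators hypothesize that a single dose of azithromycin will increase the presence of macrolide resistance determinants over a 2-week period". Section 3.5 places the matching outcome under the primary outcomes and says "Macrolide resistance will be measured from a sample of participants". Two measurements follow under that objective. One is the rectal swab cohort, analysed by DNA sequencing: "We will collect rectal swabs from 50 children at days 0, 2, 4, 6, 8, 10, 12, 14 and 180 post-treatment". The other is a rectal swab from all children at 2 years, which lies outside the two-week window. On the cohort's size, 3.2 says only "In the sub-study, 25 children per arm will be randomized"; its sample-size reasoning concerns Simpson's diversity.

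The main trial also collects what a two-week comparison needs. Section 6.2 says "Rectal swabs are collected at baseline, day 14, day 180, and 2 years after treatment", and 4.7 applies this schedule to each participant. In 3.5, under Objective 1, the plan for those swabs is "We will monitor genotypic resistance of various organisms with targeted PCR and evaluate the microbiome using next-generation sequencing". The table in 4.11 lists targeted PCR for erm, mef and mph, with sample type "Rectal and NP swabs", at days 0, 14 and 180.

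The SAP's objectives are malaria RDT positivity and the intestinal microbiome. It contains no analysis of resistance.

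**The concern.** The objective is a between-arm difference in the presence of macrolide determinants. The trial appears set to hold that information at day 14 on several hundred children or more, yet it ties the objective to 50. Nothing in the documents shows what 25 per arm can detect for a resistance outcome.

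A non-significant result from the cohort would say little about rises of 10 to 20 points. The more precise day-14 comparison would have no prespecified test, so under the SAP's own rules on unplanned analyses it could end up as hypothesis-generating or be held to alpha 0.001. The protocol presents resistance as a main open question about mass azithromycin.

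**Working it through.** **Inputs from the documents.** Cohort 25 per arm (protocol 4.3). Main trial 725 per arm (protocol 3.2) or 450 in total, 225 per arm (SAP 2.1.1 and 3). Loss to follow-up 15% (protocol 3.2): 725 × 0.85 = 616; 225 × 0.85 = 191. Seven post-dose cohort swabs up to day 14 (protocol 3.5).

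**Assumed, because not given for this outcome.** Two-sided alpha 0.05; 80% power, borrowed from the SAP's RDT calculation; control carriage 10-50%.

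**Step 1: reproduce the SAP's figure.** The SAP gives a detectable difference of -0.0659 in RDT positivity with 225 per arm and 10% in controls. For two proportions with pooled variance under the null, the detectable difference d solves

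d = 1.96·√[2p̄(1−p̄)/n] + 0.8416·√{[p0(1−p0) + p1(1−p1)]/n}, where p̄ is the mean of p0 and p1.

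With n = 225, p0 = 0.10 and p1 = 0.0341: 0.0462 + 0.0197 = 0.0659. The SAP's figure is reproduced, and it implies two-sided 0.05. The same formula is used below.

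**Step 2: one presence/absence result per child.** Example: 25 per arm, p0 = 0.30, p1 = 0.687 gives 0.277 + 0.110 = 0.387. Detectable rise in percentage points:

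| Per arm | 10% carriage | 20% | 30% | 50% |
|---|---|---|---|---|
| 25, pooled formula | 34.4 | 37.7 | 38.7 | 36.1 |
| 25, Fisher's exact | 38.5 | 41 | 41 | 39 |
| 191 (SAP size less 15%) | 10.2 | 12.6 | 13.8 | 14.1 |
| 616 (725 less 15%) | 5.3 | 6.7 | 7.5 | 7.9 |

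The 191-per-arm figure peaks at 14.3 points, at 40% carriage. The cohort rows assume no loss. With 15% loss (25 × 0.85, about 21 per arm) they rise to 38-42 points (pooled) or 42-47 (Fisher).

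**Step 3: use all seven post-dose swabs.** If a child's seven results are averaged and have within-child correlation ρ, the effective number per arm is 25 × 7 / (1 + 6ρ). At an assumed ρ of 0.5 this is 175 / 4 = 43.75, and the detectable rise is 24.6, 28.0, 29.4 and 28.3 points at 10, 20, 30 and 50% carriage. For ρ from 0.2 (effective 79.5) to 0.8 (effective 30.2) it is about 22 to 35 points at 30-50% carriage. This tests mean carriage over days 2 to 14, not carriage at day 14.

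**Step 4: one worked effect.** For a true rise from 40% to 60%, power at 25 per arm with one result per child is 24% by Fisher's exact test (29% by the pooled formula). At 191 per arm it is 98%; at 616 it is over 99%.

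**The case against.** Several points on the other side have weight.

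- **The cohort link was deliberate.** The revision history shows this objective arriving with the rectal cohort's own outcomes. Sequencing over days 2 to 14 measures a time course and a wider gene list that day-14 PCR cannot. This stands, and it is why the cohort should be kept.
- **All-child resistance is not absent from the plan.** Protocol 2.1 hypothesises more resistance genes in stool and nasopharyngeal samples, and the rectal-swab PCR is itself listed under the primary outcome. A reader might infer that a moderate rise would go unreported. The documents do not support that; what is missing is the link to Objective 3 and a prespecified test.
- **The cohort has repeated swabs and a baseline.** The 34-41 point figure assumes one result per child, an analysis the protocol does not specify. Step 3 shows how far averaging narrows the gap.
- **PCR on every child's swab is a reading, not a statement.** Section 4.11 names no subsample but does not say all swabs are tested. It lists targets by organism, and for nasopharyngeal samples 6.1 confines PCR to resistant isolates. This stands and needs confirmation.
- **Another plan exists.** The SAP lists a separate GAMIN analysis plan among the documents it reviewed. A resistance analysis may be there; it cannot be checked from these documents.

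A reader might also infer that early and late resistance cannot be compared in the same children. That is wrong: 3.5 swabs the cohort through day 180 and all children at 2 years.

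**Conclusion.** The point holds as a gap in assignment and precision. Objective 3's two-week question is tied to 25 children per arm with no stated detectable difference, while a larger comparison of the same gene class appears already scheduled and belongs to no objective-specific analysis.

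For a single result per child, the cohort's detectable rise is roughly three times that of the SAP's 450 children and five to six times that of 725 per arm. Against the averaged-swab analysis at ρ = 0.5, the SAP-size advantage is about twofold. All these figures rest on the assumed alpha, power and carriage.

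It is tempting to shorten this to a contrast of 40 points against 8, or to say that one twenty-ninth of the children are used. Both need 725 per arm (725 / 25 = 29). Protocol 2.1 and the SAP say 450, and protocol 4.6 records 407 + 43 = 450 baseline RDTs; on that size the fraction is one ninth (225 / 25) and the detectable rise is 10-15 points. Nor do the documents show that PCR should replace sequencing as the test of Objective 3: that would change both assay and endpoint.

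**What to change.** 1. In protocol 3.5 and the SAP, add to Objective 3 a between-arm comparison of erm/mef/mph presence on the day-14 rectal swab, in all randomised children with PCR results, adjusted for the day-0 result. Report day 180 as persistence.
2. Keep the sequencing cohort for the day 2-14 time course and the broader gene list, and say how the two results will be read together.
3. In 3.2, state the detectable difference for both analyses, with the assumed carriage, alpha and power, using a reconciled main-trial size (450 or 1,450).
4. Confirm in 4.11 that the PCR is run on every child's rectal swab and yields a per-child presence result. If it is meant for a subset, say which.

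If item 4 is confirmed, the cost is protocol and SAP wording: no new visit, swab or assay. The downside is that PCR covers three gene families, informs the two-week window at day 14 only, and is a different assay from the cohort's sequencing, so the two results are complementary rather than interchangeable.
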